### **F2 Statistical Methods**

The primary outcome of interest is the LV end-systolic volume. Secondary outcomes include quality-of-life (KCCQ-12), functional performance (6-minute hall walk distance) and a prognostic biomarker (serum NT-proBNP). We will perform **t-tests** to assess for differences in the % change from baseline in primary and secondary endpoints between treatment groups. Sub-analyses will evaluate for effect modification by subgroups based on ischemic vs. non-ischemic cardiomyopathy, sex, and magnitude of RV-LV offset based on ECG. We prespecify evaluation of the subgroup with ECG optimized RV-LV offset  $\geq 40$  msec. A two-tailed p-value 0.05 will be considered as threshold for statistical significance.

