## **C2 Rationale for the Selection of Outcome Measures**

The primary outcome is echocardiographic LV end-systolic volume. LV end-systolic volume is a reliable surrogate for clinical outcomes in clinical heart failure trials. Secondary outcomes include quality-of-life (KCCQ-12), functional performance (6-minute hall walk distance) and a prognostic biomarker (serum NT-proBNP). KCCQ-12 and 6-minute hall walk are standard metrics to assess quality-of-life and functional status in heart failure research. Serum NT-ProBNP strongly predicts improvement in cardiac function and favorable prognosis after CRT.

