## **D2 Subject Selection and Withdrawal**

### **2.a Inclusion Criteria**

1. Patients  $\geq 18$  years of age who are able to give consent.
2. Diagnosis of systolic heart failure.
3. Planned to undergo new CRT device implant (or upgrade of preexisting pacemaker or defibrillator device to CRT system) for standard clinical indications.
4. Expected to have over 95% heart beats resynchronized with CRT (absence of competing arrhythmias or plans to not immediately activate CRT therapy).

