## E2 Schedule of Measurements

The baseline evaluation will encompass one, two or more visits in the time window 6 weeks prior to 2 weeks after CRT device implant/upgrade date. If the patient passes the eligibility screening and signs informed consent, their baseline evaluation will include echocardiogram, quality-of-life questionnaire, 6-minute hall walk, blood test, vital signs, ECGs, device interrogation and baseline demographic and medical history including chart review. After CRT device implant, participants will undergo physiologic evaluations at various (up to 10 or more) RV-LV offset settings including ECGs and echocardiography. The randomized CRT pacing assignment will be programmed.

The follow-up evaluation (usually 3-12 months) will encompass one or more visits and include echocardiography, quality-of-life questionnaire, 6-minute hall walk test, blood test, vital signs, ECGs, device interrogation, and follow-up medical history including chart review. The patients will continue to be in extended follow-up through review of their medical charts till the end of the study (12 months from date of CRT implant/upgrade of the the last study participant).

Table 2.  

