## **F Statistical Plan**

### **F1 Sample Size Determination and Power**

We plan to randomize 200 patients that may require enrollment of up to **250 patients**. This gives us 80% power to detect a between-treatment difference of  $\geq 2 \pm 5\%$  in the % reduction in LV end-systolic volume from baseline with a 2-sided  $\alpha$ -error 0.05. Previous studies have shown that a reduction in LV end-systolic volume from baseline is associated with an improvement in clinical outcomes. As both the study and control arms will receive CRT, albeit with different approach to programming RV-LV offset, any statistical difference in reverse cardiac remodeling between the two RV-LV offset programming strategies will be clinically important.

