## **G Data Handling and Record Keeping**

### **G1 Confidentiality and Security**

- No specimens, records, or data will be collected from anyone not participating in the study.
- The human study subjects will provide baseline demographic and historical data related to their heart failure and related medical illnesses. This will be collected from their medical chart, patient interview, and patient questionnaire. The subjects will also provide echocardiography, quality-of-life questionnaire, 6-minute hall walk, blood sample, ECG, CRT device interrogation, and clinical information at baseline and follow-up.

- 
- Only the research staff and the data safety monitoring committee will have access to identifiable private information. Password-secured anonymized data will be stored on secure Washington University server (WUSTL BOX) and in REDCap, and kept in confidential study binders maintained by the Washington University Cardiovascular Research core in a locked cabinet in a locked suite.
  - The data related to the research project will be collected and managed using the standard protocols to protect PHI. Use of patient identifying information will be minimized and participant information will be identified by study ID number. The collection forms will be labeled only with the study ID number.

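### F2 tests all four endpoints with unadjusted t-tests on % change; adding baseline for LV end-systolic volume and a log-scale ANCOVA for NT-proBNP would improve efficiency at almost no cost

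*Combined protocol and SAP*

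**What the plan says.** Section F2 (Statistical Methods) names LVESV as primary, and KCCQ-12, 6-minute walk distance and serum NT-proBNP as secondary outcomes. One method covers all four: t-tests "to assess for differences in the % change from baseline in primary and secondary endpoints between treatment groups". It adds: "A two-tailed p-value 0.05 will be considered as threshold for statistical significance". No section names a baseline covariate, a log transformation or a rank-based alternative.

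Section F1 states its power on the same scale as the F2 test, for a between-arm difference in the percentage "reduction in LV end-systolic volume from baseline with a 2-sided" error of 0.05.

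The baselines exist. In section E2, once patients are eligible and have consented, "their baseline evaluation will include echocardiogram, quality-of-life questionnaire, 6-minute hall walk, blood test" and other items. Section G1 repeats this for baseline and follow-up: "The subjects will also provide echocardiography, quality-of-life questionnaire, 6-minute hall walk, blood sample". The study calendar (Table 2) agrees. Section C2 justifies the biomarker: "Serum NT-ProBNP strongly predicts improvement in cardiac function and favorable prognosis after CRT".

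The documents give no distribution, SD or expected effect for the three secondary endpoints.

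**The concern.** One arithmetic-percentage test is applied to four measures that are likely to behave differently, and the baselines are used only as denominators.

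- **LVESV.** If relative change depends on baseline volume, an unadjusted t-test leaves that explainable variance in the error term. F1 plans for 80% power with no stated allowance for loss after randomisation, so there is little to spare.
- **NT-proBNP.** Percentage change cannot fall below -100% but has no upper limit. If the marker is right-skewed, a few large rises can dominate an arm mean and inflate its variance. A baseline covariate alone does not remove this; the log scale does.
- **KCCQ-12 and walk distance.** Percentage change gives extra weight to patients with low baselines, and the eligibility criteria set no minimum for either.

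At stake is the chance of detecting a true effect, above all on NT-proBNP.

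**Working it through.** **1. F1's own figure.** Inputs from F1 and section 2.e: difference 2 points, SD 5 (reading the ± figure as an SD), 200 randomised 1:1 so 100 per arm, two-sided 0.05. The standardised effect is 2/5 = 0.4.

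- n per arm = 2(1.960 + 0.842)²/0.4² = 98.1, so 99 per arm or 198 in total, against 200 planned.
- Power at 100 per arm: 0.4 × √(100/2) = 2.828, and Φ(2.828 − 1.960) = 80.7%. With the noncentral t it is 80.4%.

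F1 reproduces, and F1 and F2 are consistent.

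**2. LVESV with baseline in the model.** If % change and baseline have correlation r (assumed), the residual SD is 5√(1 − r²). Power = Φ(2/(SD × √(2/100)) − 1.960):

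| r | Residual SD | Power | Gain over 80.7% |
|---|---|---|---|
| 0.1 | 4.97 | 81.1% | 0.4 |
| 0.2 | 4.90 | 82.3% | 1.6 |
| 0.3 | 4.77 | 84.3% | 3.5 |
| 0.4 | 4.58 | 87.0% | 6.3 |
| 0.5 | 4.33 | 90.4% | 9.7 |

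At r = 0, simulation shows a change of 0 to −0.3 points.

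**3. NT-proBNP.** All inputs are assumptions: lognormal values with log-SD s of 0.8 to 1.2, baseline/follow-up correlation r on the log scale of 0.5 to 0.8, and 100 per arm. The effect is set at 0.398 SD of the log ratio, which gives an unadjusted t-test on the log ratio 80% power.

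- SD of log ratio = s√(2(1 − r)). The effect therefore runs from 0.398 × 0.8 × √0.4 = 0.201 (an 18% reduction, 1 − e^−0.201) to 0.398 × 1.2 × 1 = 0.478 (a 38% reduction).
- Log-ANCOVA residual SD = s√(1 − r²), so its standardised effect is 0.398 × √(2/(1 + r)). At r = 0.5 this is 0.460, and power is Φ(0.460 × 7.071 − 1.960) = 90%. At r = 0.8 it is 0.420, and power is 84%.
- The % change test has no simple closed form and was simulated. At log-SD 1.0:

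| r | Implied reduction | % change t-test | Log-ANCOVA |
|---|---|---|---|
| 0.5 | 33% | 60% | 90% |
| 0.7 | 27% | 68% | 86% |
| 0.8 | 22% | 72% | 84% |

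Over the whole grid, power is about 54-75% for the planned test, 59-78% for % change with baseline added, and 83-90% for log-ANCOVA. If the effect is instead set so that log-ANCOVA has 80% power, the planned test has 42-69%. With gamma instead of lognormal data, log-ANCOVA was higher in all 18 settings tried.

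Milder assumptions shrink the gap. At r = 0.9 it is about 4-7 points. If the follow-up/baseline ratio is independent of baseline with log-SD 0.2-0.3, it is 1-2 points. Log-ANCOVA was not worse in any case tried, beyond simulation error.

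**4. Type I error.** Simulated rejection under the null was 4.0-5.3% for the NT-proBNP % change t-test and 4.9-5.3% for log-ANCOVA. For LVESV it was 5.1% (t-test) and 5.2% (with baseline).

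**5. KCCQ-12 and walk distance.** The direction depends on the assumed model. The ranges below come from one set of simulations:

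| Endpoint and model | % change t-test | Raw-scale ANCOVA |
|---|---|---|
| KCCQ-12, additive | 17-44% | about 79% |
| KCCQ-12, proportional | 79-80% | 72-73% |
| Walk, additive | 35-54% | 78-80% |
| Walk, proportional | 79-81% | 75-76% |

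A second set, with other assumptions, gave smaller additive losses (% change at 44-69% for KCCQ-12 and 57-65% for walk). Over both sets, raw-scale ANCOVA loses 2-8 points when the ratio is independent of baseline.

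**The case against.** The strongest reply is that nothing in the plan is wrong. The test is valid, F1 and F2 match, F1 claims no power for the secondary endpoints, and every gain above rests on assumed distributions. That stands, and it limits the point to efficiency. It does not remove it, because the baselines are already being collected and the suggested analyses lose almost nothing where they fail to help.

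Four further points stand:

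- The largest NT-proBNP gaps go with the largest assumed effects. A 38% reduction between two active CRT arms is a lot to expect, and with low variability the loss is trivial.
- The LVESV gain is conditional. No figure in the documents shows that % change depends on baseline, and gains well above 10 points would need a stronger correlation than is assumed here.
- Moving NT-proBNP to the log scale changes the quantity reported.
- Whether an SD of 5 is realistic is a separate and larger question. At an SD of 10, power for 2 points is 29%, which no baseline covariate would restore.

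A reader might infer that the planned test is the one most likely to miss an NT-proBNP effect. It is not: in the same lognormal settings a t-test on raw change has only about 33-54% power. A reader might also infer that KCCQ-12 and walk distance should move to raw-scale ANCOVA. The documents do not say whether change is additive or proportional, and under the second that move loses power.

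**Conclusion.** The point holds as an efficiency weakness in F2. It does not show an invalid primary analysis, an inflated type I error or a wrong sample size; the documents support none of those readings.

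- **LVESV:** adding baseline costs at most about 0.3 power points and gains about 0.5 to 10 if the correlation with % change is 0.1 to 0.5. This takes F1's SD of 5 and 100 analysed per arm as given.
- **NT-proBNP:** under assumed right skew with moderate correlation, the planned test has about 54-75% power against 83-90% for log-ANCOVA. The direction was consistent; the size is not fixed by the documents and can be as small as 1-2 points.
- **KCCQ-12 and walk distance:** undetermined, so no change is required.

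Confidence is medium, because every distribution and correlation is assumed.

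**What to change.** Reword F2 before any unblinded data are seen:

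1. **LVESV (primary).** Keep % change from baseline as the outcome. Replace the t-test by a linear model with arm and baseline LVESV, stating in advance whether baseline enters raw or logged. The effect remains a difference in percentage points, so F1 stands.
2. **NT-proBNP.** Prespecify ANCOVA of log follow-up on arm and log baseline, reported as a geometric mean ratio with its confidence interval. Keep the % change t-test as a sensitivity analysis.
3. **KCCQ-12 and walk distance.** No change required.

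The cost is a text change to one section, with no new data, visits or patients. The one real trade-off is that the NT-proBNP effect becomes a ratio of geometric means instead of a difference in mean % change. It can still be read as a percentage difference between arms.

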## **G Data Handling and Record Keeping**

### **G1 Confidentiality and Security**

- No specimens, records, or data will be collected from anyone not participating in the study.
- The human study subjects will provide baseline demographic and historical data related to their heart failure and related medical illnesses. This will be collected from their medical chart, patient interview, and patient questionnaire. The subjects will also provide echocardiography, quality-of-life questionnaire, 6-minute hall walk, blood sample, ECG, CRT device interrogation, and clinical information at baseline and follow-up.

- 
- Only the research staff and the data safety monitoring committee will have access to identifiable private information. Password-secured anonymized data will be stored on secure Washington University server (WUSTL BOX) and in REDCap, and kept in confidential study binders maintained by the Washington University Cardiovascular Research core in a locked cabinet in a locked suite.
  - The data related to the research project will be collected and managed using the standard protocols to protect PHI. Use of patient identifying information will be minimized and participant information will be identified by study ID number. The collection forms will be labeled only with the study ID number.

## **G2 Records Retention**

The collection forms will be kept in confidential study binders at the Washington University Cardiovascular Research core in a locked cabinet in a locked suite. The data will be entered electronically and stored on secure server (WUSTL Box and REDCap).

# **H Study Monitoring, Auditing, and Inspecting**

## **H1 Study Monitoring Plan**

In compliance with the Washington University Institutional Data and Safety Monitoring Plan, the Data and Safety Monitoring Committee (DSMC) will meet to review data at least annually beginning six months after accrual has begun. The report will be prepared by the study statistician with assistance from the study team and will be reviewed by the DSMC. The report will include:

- HRPO protocol number, protocol title, Principal Investigator name, research coordinator name, and statistician.
- Date of initial HRPO approval, date of most recent consent HRPO approval/revision, date of HRPO expiration, study status, and phase of study.
- History of study including summary of substantive amendments; summary of accrual suspensions including start/stop dates and reason; and summary of protocol exceptions, error, or breach of confidentiality including start/stop dates and reason.
- Study-wide target accrual and study-wide actual accrual.
- Protocol activation date.
- Average rate of accrual observed in year 1, year 2, and subsequent years
- Expected accrual end date
- Objectives of protocol with supporting data and list the number of participants who have met each objective.
- Measures of efficacy.
- Abstract submissions/publications
- Summary of any recent literature that may affect the safety or ethics of the study
- Additional information the DSMC may request

The following information will be monitored and provided to the DSMC:

- Enrollment and follow-up
- Adverse events occurring during follow-up, including hospitalizations and death

The DSMC will have complete access to the raw study data throughout the duration of the study.

The DSMC will have complete discretion for terminating the study for concerns of patient safety.

---

The investigator and the study coordinators will be responsible to report all Adverse Events, Serious Adverse Events (deaths, hospitalizations, life threatening events and any Unanticipated Problems) to the data safety monitoring committee and IRB as described above.

## **I Study Administration**

### **I1 Organization and Participating Centers**

This is a single centre study at Washington University/Barnes-Jewish Hospital.

### **I2 Funding Source and Conflicts of Interest**

This study is funded through Divisional support and American College of Cardiology Presidential Career Development Award to the PI.

### **I3 Subject Stipends or Payments**

None

### **I4 Study Timetable**

Subjects will be enrolled in 2019-2021 and complete study related follow-up by 2022.

## **J Publication Plan**

The trial results will be submitted for publication in an reputed peer-reviewed cardiology journal.

